10.3 Centralized Radiology Review

Radiologic images to determine response status (baseline and subsequent exams) will be transmitted to the Coordinating Center for centralized, independent review and confirmation of response assessment when a patient goes off treatment.

11 CORRELATIVE STUDIES

11.1 Participation in Correlative Studies

Section 1.4 outlines the plans and rationale for the correlative studies. Participation in the correlative studies is a study requirement. Samples for correlative studies will be collected at the participating study site.

11.4.1 [REDACTED]

11.6 Tracking and Collection of Samples

Collection and distribution of all samples will be logged by the study team at the participating site in OnCore.

- K. Brain imaging only required for patients with brain metastasis diagnosed and treated prior to initiation of study treatment. The imaging used at baseline should be used at each subsequent imaging time point.
- L. Counting from C1D1, for the first 24 weeks, during Week 6, 12, 18, and 24 (±1 week), or sooner, if clinically indicated, until documentation of confirmed progression. After 24 weeks, tumor assessments must be performed every 9 weeks counting from C1D1 (during Week 33, 42, 51, 60, etc.) (±1 week), or sooner if clinically indicated, until documentation of confirmed PD. Responses and PD must be confirmed at least 4 weeks later (usually at the next tumor assessment).
- M. PROs will be administered every day 1 of every cycle starting at C1D1 and 30 days after last dose of study drug until patient enters the extended follow-up period. During the extended follow-up period PROs will be administered every 3 months (see Section [1.4.1](#)).
- N. FACIT/HADS questionnaire will be administered at baseline, C1D1, C2D1, C3D1, then every other cycle beginning at C5 and beyond, end of study, and the first extended follow-up visit (see Section [1.4.1](#)).
- O. Collect correlative whole blood urine, and vaginal swab samples any time after consent and before C1D1 prior to the initiation of any study treatment. See also Section [11](#).
- P. An optional additional blood sample will be collected for DNA ancestral analysis. See [Section 11.3.1](#)
- Q. Collect correlative whole blood at the conclusion of therapy if prior to 90 days. See also Section 11
- R. Capture survival status approximately every 3 months during the extended follow-up period. During the extended follow-up period, data may be obtained by record review or patients may be contacted by phone for report of disease status, new treatment and/or survival status approximately every 3 months.
- S. Lenvatinib administered orally (PO) once daily (QD) during each 21-day cycle For lenvatinib instructions refer to Sections [6.2](#), [7.3](#), and [9.1](#).
- T. Pembrolizumab administered by IV infusion on day 1 of each 21-day cycle. For pembrolizumab instructions refer to Sections [6.2](#), [7.4](#), and [9.2](#).

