6.5 Duration of Follow-Up

6.5.1 Initial AE Evaluation Period after Discontinuation of Treatment

Patients who discontinue treatment **for any reason other than death or their choice to withdraw from all study follow-up** remain on study in follow-up status for an initial 30-day AE evaluation period following the last dose of study treatment. This 30-day post-treatment follow-up period is meant to capture resolution or stabilization of ongoing treatment-related AEs or evolution of new treatment-related AEs.

The initial AE follow-up period may be extended if new or worsening treatment-related AEs require longer observation. Similarly, the initial AE follow-up period may end early in the event of death, patient request to withdraw from follow-up, or initiation of new anticancer therapy.

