6.5.2 Ongoing Follow-up

Patients who discontinue treatment with ongoing SD, PR, or CR (see Section 10) remain in follow-up status for PFS by reported clinical status every 3 months until one of the following occurs: disease progression, relapse, or death.

All patients will be followed for OS status every 3 months, until death or off-study.

The primary reason(s) for a patient's discontinuation from study treatment and from follow-up status are to be recorded in the source documents and the OnCore database.

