8.3 Time Period and Grade of AE Capture

All AEs, SAEs, and UPs will be captured as follows and recorded in the study database.

All AEs, SAEs, and UPs will be evaluated from the time the informed consent form is signed through the follow-up visit 30 ± 15 days after the last administered component of study regimen (see Section [6.5.1](#)). The AE safety follow-up period may be truncated if the patient begins other antineoplastic therapy during that time. Collection of irAEs will continue at survival status assessment time points (every 3 months ± 15 days) as long as survival status assessment continues.

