9.2.10 Warnings and Precautions

Severe and Fatal Immune-Mediated Adverse Reactions

Pembrolizumab is a monoclonal antibody that belongs to a class of drugs that bind to either the programmed death-receptor 1 (PD-1) or the PD-ligand 1 (PD-L1), blocking the PD-1/PD-L1 pathway, thereby removing inhibition of the immune response, potentially breaking peripheral tolerance and inducing immune-mediated adverse reactions. Important immune-mediated adverse reactions listed may not include all possible severe and fatal immune-mediated adverse reactions.

Immune-mediated adverse reactions, which may be severe or fatal, can occur in any organ system or tissue and can affect more than one body system simultaneously. Immune-mediated adverse reactions can occur at any time after starting treatment with a PD-1/PD-L1 blocking antibody. While immune-mediated adverse reactions usually manifest during treatment with PD-1/PD-L1 blocking antibodies, immune-mediated adverse reactions can also manifest after discontinuation of PD-1/PD-L1 blocking antibodies. Early identification and management of immune-mediated adverse reactions are essential to ensure safe use of PD-1/PD-L1 blocking antibodies. Monitor patients closely for symptoms and signs that may be clinical manifestations of underlying immune-mediated adverse reactions. Evaluate liver enzymes, creatinine, and thyroid function at baseline and periodically during treatment. In cases of suspected immune-mediated adverse reactions, initiate appropriate workup to exclude alternative etiologies, including infection. Institute medical management promptly, including specialty consultation as appropriate.

Withhold or permanently discontinue pembrolizumab depending on severity. In general, if pembrolizumab requires interruption or discontinuation, administer systemic corticosteroid therapy (1 to 2 mg/kg/day prednisone or equivalent) until improvement to grade 1 or less. Upon improvement to grade 1 or less, initiate corticosteroid taper and continue to taper over at least 1 month. Consider administration of other systemic immunosuppressants in patients whose immune-mediated adverse reactions are not controlled with corticosteroid therapy.

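### Section 8.3 lets AE and SAE capture close as early as day 15 against the 30 days in 6.5.1, and the passages describing the 3-monthly contacts omit the irAE collection that 8.3 requires

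*Combined protocol and SAP*

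**What the plan says.** **End of AE capture.** Section 8.3 evaluates AEs, SAEs and unanticipated problems from consent "through the follow-up visit 30 ± 15 days after the last administered component of study regimen", and refers to Section 6.5.1 for that period. Section 6.5.1 says that patients who stop treatment "remain on study in follow-up status for an initial 30-day AE evaluation period" and attaches no tolerance to the 30 days. Both sections allow change. In 8.3, "The AE safety follow-up period may be truncated if the patient begins other antineoplastic therapy during that time". In 6.5.1, the period may end early for death, withdrawal from follow-up or new anticancer therapy, and "The initial AE follow-up period may be extended if new or worsening treatment-related AEs require longer observation".

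**After that visit.** Section 8.3 continues: "Collection of irAEs will continue at survival status assessment time points (every 3 months ± 15 days"), for as long as survival is being assessed. Two other places describe those contacts. Section 6.5.2 asks for progression status by clinical report in patients who stopped without progression, and adds: "All patients will be followed for OS status every 3 months, until death or off-study". Footnote R of the study calendar says that "data may be obtained by record review or patients may be contacted by phone for report of disease status, new treatment and/or survival status".

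**Why late events are relevant.** Section 9.2.10 warns that "immune-mediated adverse reactions can also manifest after discontinuation of PD-1/PD-L1 blocking antibodies".

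**The concern.** Two passages that should define one AE window define different ones, and the shorter can be half the length of the other. Separately, a duty stated in 8.3 is not repeated where sites are told what to do at the contacts on which it depends. The *and/or* in footnote R, together with record review as an accepted source, means that a contact recording survival alone satisfies the calendar and leaves 8.3 unmet.

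The incidence of treatment-related AEs is a secondary objective (2.2.2), and Section 3.1 names safety in an under-represented population as a purpose of the trial. Section 13.1 analyses time to toxicity with censoring. A crude incidence makes no allowance for one patient being observed to day 15 and another to day 45. The time-to-event analysis can allow for it only if the true closing date is recorded and used for censoring, and if early closure is unrelated to the patient's risk. Section 13.1 does not state the censoring date for these outcomes. With up to 10 sites, practice can also differ by site.

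**Working it through.** The plan gives no figure on this point to reproduce. The check is day arithmetic and a comparison of the passages.

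**1. The AE window.** Inputs: 30 ± 15 days (8.3) and 30 days (6.5.1).

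- Earliest compliant close: 30 − 15 = day 15.
- Latest compliant close: 30 + 15 = day 45.
- Shortfall against 6.5.1 with a day-15 visit: 30 − 15 = 15 days, or 15/30 = 50%.
- Excess with a day-45 visit: 45 − 30 = 15 days.
- Longest to shortest compliant window: 45/15 = 3.

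**2. An event with onset on day 20, after a day-15 visit.**

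- *Immune-related:* 8.3 makes it due at the first survival contact. The documents do not say when the 3 months start, so take 3 months as 91 days (an assumption) with the ± 15 days of 8.3. Counted from the last dose, the contact falls on day 91 − 15 = 76 to 91 + 15 = 106. Counted from a day-15 visit, it falls on day 91 to 121. Counted from a day-30 visit, it falls on day 106 to 136.
- *Not immune-related:* 8.3 has no later collection point. The 6.5.1 extension could reach the event, but only if the site learns of it, and after a closing visit nothing scheduled asks for it.

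**3. What is collected at the 3-monthly contacts.**

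| Place | Content | irAEs named? |
|---|---|---|
| 8.3 | irAE collection continues | Yes |
| 6.5.2 | Progression and survival status | No |
| Footnote R | Disease status, new treatment, survival, in any combination | No |
| Footnote G (AE row) | CTCAE grading; points to Section 8 for expedited reporting | No |

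Neither 6.5.2 nor footnote R cross-refers to 8.3. Footnote C, on 30-day and extended follow-up, has no visible anchor in the calendar as read here, so a column may be absent from this copy. Nothing is therefore inferred from missing AE marks in the table. The comparison uses only the section and footnote text.

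**4. Size.** The documents give no rate of new events after the last dose, so no count of missed events can be derived.

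**The case against.** The case for leaving the text alone has several parts.

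- *Section 8.3 is binding.* The other passages omit irAE collection without contradicting it, and footnote R annotates the survival row, where silence on AEs is weak evidence. This stands. A reader might infer that late treatment-related events are missed; the documents support only that they may be under-collected.
- *Patient contact is already planned.* Footnote M schedules patient-completed questionnaires 30 days after the last dose and every 3 months in extended follow-up. This stands against any suggestion that follow-up is by record review alone. But the questionnaires are not AE collection, and no text links the two.
- *The window is symmetric and can be extended.* A day-45 visit lengthens capture as much as a day-15 visit shortens it, and the early-end reasons in 6.5.1 do not include an early visit. This stands as far as it goes. Longer capture in one patient does not recover an event lost in another, and extension depends on the event being known.
- *Late serious irAEs are covered.* A reader might infer that they escape expedited reporting because 8.3 ends SAE evaluation at the follow-up visit. The SAE definition in 8.1.2 has no time limit, and Table 5 runs from the site's awareness with no end date. The inference is not supported; a clarifying sentence is all that is needed.
- *Drug persistence.* A reader might argue from pembrolizumab's slow clearance that events must be lost. Fraction of drug remaining is not an event rate, and the late immune events of that drug are the ones 8.3 does follow. For lenvatinib, the half-life of about 28 hours in 9.1.7 gives 15 × 24 / 28 = 12.9 half-lives by day 15, which if anything tempers concern about that drug. Neither figure measures an under-count.

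**Conclusion.** The point holds as an inconsistency and an omission with a plausible effect on safety data; no loss of events is demonstrated. Followed as written, 8.3 can close capture of AEs, SAEs and unanticipated problems up to 15 days short of the period in 6.5.1, and compliant windows can differ threefold between patients. The clear gap is for non-immune treatment-related events between an early visit and day 30. For irAEs the plan does require collection; the risk is that sites following 6.5.2 or footnote R alone do not carry it out.

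This rests on reading the ± 15 days as a tolerance that also moves the end of capture, which is what the 8.3 wording does. If the sponsor meant only the visit date to move, with evaluation still running to day 30, the text should say so. An average number of days lost would need a distribution of visit days, which the documents do not give. The primary endpoint is unaffected. The correction is worth making because it bears on objective 2.2.2 and the time-to-toxicity analysis and is cheap.

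**What to change.** 1. Reconcile 8.3 with 6.5.1 so that AE, SAE and unanticipated-problem capture does not close before day 30, except for the early-end reasons already in 6.5.1. Either a visit window of 30 to 45 days or a phone check at day 30 after an earlier visit would do this. The phone check could be combined with the day-30 questionnaire in footnote M.
2. Name irAEs in 6.5.2 and footnote R, or cross-refer both to 8.3. Ask about them at the 3-monthly patient contact already planned for questionnaires.
3. As a clarification only, state that a serious irAE found at a later contact is reported under Table 5.

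The cost is wording in three places, slightly less flexible timing of the safety visit (or one phone call) and one added question per follow-up contact. No treatment rule changes.

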13 STATISTICAL CONSIDERATIONS

13.1 Study Design and Analysis

Primary Analysis: The binary outcome ORR: will be estimated with a sample proportion and 95% Wilson confidence intervals. The ORR will be estimated in unadjusted and adjusted manners, where in the latter case we use logistic regression to model the outcome against fixed effects for patient characteristics and disease biomarkers, using a Bernoulli distribution and logit link function, including a set of measurements that minimize the Bayesian Information Criterion.

Secondary Analyses: OS is calculated as the time between treatment start date until date of death from any cause or until censoring. PFS is calculated as the time between treatment start date until occurrence of disease progression or until censoring. The Kaplan-Meier product limit approach will be used to estimate step functions for OS and PFS. Proportional hazard modeling will be used to estimate mean survival time in both unadjusted and adjusted manners, where in the latter case we account for patient characteristics and disease biomarkers.

Safety Analyses: Times to toxicity, dose reduction, or drug discontinuation will be used as safety outcomes. Each measure is calculated as the time between treatment start date until event occurrence or until censoring. These measures will be summarized using proportional hazards regression, and visually present the event curves with cumulative incidence curves.

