2.2 Secondary Objectives

- 2.2.1 Determine median PFS in the study population
- 2.2.2 Determine the incidence of treatment-related AEs in the study population
- 2.2.3 Determine the number of patients who discontinue treatment due to treatment-related AEs

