3.3 Secondary Endpoints

- 3.3.1 Proportion of patients who are alive and have not had disease progression or relapse following last dose of study treatment
- 3.3.2 Using criteria in the National Cancer Institute Common Terminology Criteria for Adverse Events Version 5.0 (CTCAE v5.0), all AEs captured as described in Section [8.4](#).
- 3.3.3 Number of patients who discontinue treatment due to treatment-related AEs.

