9.2.11 Adverse Events

The safety of pembrolizumab in combination with lenvatinib (20 mg orally once daily) was investigated in KEYNOTE-146, a single-arm, multicenter, open-label trial in 94 patients with endometrial carcinoma whose tumors had progressed following one line of systemic therapy and were not MSI-H or dMMR. The median duration of study treatment was 7 months (range: 0.03 to 37.8 months). The median duration of exposure to pembrolizumab was 6 months (range: 0.03 to 23.8 months).

Pembrolizumab was continued for a maximum of 24 months; however, treatment with lenvatinib could be continued beyond 24 months. Fatal adverse reactions occurred in 3% of patients receiving pembrolizumab and lenvatinib, including gastrointestinal perforation, reversible posterior leukoencephalopathy syndrome (RPLS) with intraventricular hemorrhage, and intracranial hemorrhage. Serious adverse reactions occurred in 52% of patients receiving pembrolizumab and lenvatinib.

Serious adverse reactions in $\geq 3\%$ of patients were hypertension (9%), abdominal pain (6%), musculoskeletal pain (5%), hemorrhage (4%), fatigue (4%), nausea (4%), confusional state (4%), pleural effusion (4%), adrenal insufficiency (3%), colitis (3%), dyspnea (3%), and pyrexia (3%). Pembrolizumab was discontinued for adverse reactions (grade 1-4) in 19% of patients, regardless of action taken with lenvatinib.

The most common adverse reactions ($\geq 2\%$) leading to discontinuation of pembrolizumab were adrenal insufficiency (2%), colitis (2%), pancreatitis (2%), and muscular weakness (2%).

Adverse reactions leading to interruption of pembrolizumab occurred in 49% of patients; the most common adverse reactions leading to interruption of pembrolizumab ($\geq 2\%$) were: fatigue (14%), diarrhea (6%), decreased appetite (6%), rash (5%), renal impairment (4%), vomiting (4%), increased lipase (4%), weight loss (4%), nausea (3%), increased blood alkaline phosphatase (3%), skin ulcer (3%), adrenal insufficiency (2%), increased amylase (2%), hypocalcemia (2%), hypomagnesemia (2%), hyponatremia (2%), peripheral edema (2%), musculoskeletal pain (2%), pancreatitis (2%), and syncope (2%). [Table 7](#) and

Table 8 summarize adverse reactions and laboratory abnormalities, respectively, in patients on pembrolizumab in combination with lenvatinib.

Table 7. Adverse Reactions Occurring in $\geq 20\%$ of Patients with Endometrial Carcinoma in KEYNOTE-146

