13.2 Sample Size/Accrual Rates

As the goal of this proposal is to estimate ORR, we will not formally power for hypothesis testing. With 100 subjects (and conservatively assuming a 0.5 ORR for maximum variability), we would be able to estimate the ORR with a margin of error of ± 0.1 .

This study is expected to be open to accrual at a total of 10 sites across the US within 24 months of its initial approval at the coordinating site, VCU Massey Cancer Center. Each site is anticipated to accrue an average of 1 patient every 2 to 3 months. The total period of study recruitment is therefore anticipated to occur over a period of 25 to 42 months, with recruitment complete by July 1, 2025.

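### Section 13.1 omits death from the PFS event, so the analysis as written estimates time to progression instead of the median PFS in objective 2.2.1

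*Combined protocol and SAP*

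**What the plan says.** Objective 2.2.1 is to "Determine median PFS in the study population". The only time-to-event definition of PFS is in section 13.1, under Secondary Analyses: "PFS is calculated as the time between treatment start date until occurrence of disease progression or until censoring". The sentence before it reads: "OS is calculated as the time between treatment start date until date of death from any cause or until censoring". Both curves are to be estimated by Kaplan-Meier. No section gives a censoring date or rule for either outcome.

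Two other places bear on whether death counts:

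- Endpoint 3.3.1 is "Proportion of patients who are alive and have not had disease progression or relapse following last dose of study treatment".
- Section 6.5.2 says that patients who stop treatment with stable disease or a response "remain in follow-up status for PFS by reported clinical status every 3 months until one of the following occurs: disease progression, relapse, or death".

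**The concern.** In adjacent sentences, one outcome has death as its event and the other has only progression. If progression is the sole event, a patient who dies without documented progression can leave the Kaplan-Meier risk set only as a censored observation. The result is a time-to-progression curve labelled PFS.

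Such deaths are plausible. Section 9.2.11 reports for the earlier single-arm trial of this combination: "Fatal adverse reactions occurred in 3% of patients receiving pembrolizumab and lenvatinib". Eligibility extends to ECOG 2. Note L to the section 12 calendar asks for progression to be confirmed at least 4 weeks later, and 13.1 does not say whether progression must be confirmed to count, so a patient who dies in between could be left with no event. After treatment stops without progression, disease status may come from a phone call or record review, so progression before death may go undocumented. Censoring those deaths would be informative.

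Median PFS is the first secondary objective, and sections 1.3 and 1.3.1 set out PFS results from other trials. A curve that leaves out deaths invites a false comparison with them. Endpoint 3.3.1 adds a second mismatch: it is a proportion with no time point, while 2.2.1 asks for a median.

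**Working it through.** **1. The plan's own figure.** The plan states no figure for PFS. Its only design figure is the ±0.1 margin for ORR in section 13.2 (n = 100, ORR 0.5). The Wald half-width is 1.96 × √(0.5 × 0.5/100) = 0.098, and the Wilson half-width is 0.096. Both round to 0.1. Nothing below changes this figure.

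**2. Formula.** Assume constant hazards, with total first-event hazard λ, and let q be the share of first events that are deaths without progression.

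- Median PFS = ln 2/λ.
- If those deaths are censored on the date of death, the curve estimates exp(−(1−q)λt), with median ln 2/((1−q)λ).
- The ratio of the two medians is 1/(1−q). At the true PFS median the curve reads 0.5^(1−q) instead of 0.50.

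**3. Value of q.** The documents do not give it. The only anchor is the 3% in section 9.2.11, a share of patients in another trial that covers fatal adverse reactions only. To turn it into a share of events, divide by the share of patients with a PFS event, assumed here to be 70–100%: 0.03/1.0 = 3.0% and 0.03/0.7 = 4.3%.

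**4. Results.**

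| q | Basis | Median multiplied by |
|---|---|---|
| 3.0% | anchor, all patients have an event | 1/0.970 = 1.031 |
| 4.3% | anchor, 70% have an event | 1/0.957 = 1.045 |
| 10% | assumed, no support in the documents | 1/0.90 = 1.111 |
| 20% | assumed, no support in the documents | 1/0.80 = 1.250 |

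A simulation of 200,000 patients with an assumed median PFS of 7 months gave medians of 7.18, 7.79 and 8.73 months at q = 3%, 10% and 20%. The formula gives 7.22, 7.78 and 8.75.

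**5. At the size of this trial.** The simulation used n = 100 and 1,000 trials for each combination of q (3%, 10%, 20%) and assumed median PFS (20, 30, 40 weeks). Follow-up was uniform over 52–156 weeks (assumed), and progression was seen only at the scans in note L (weeks 6, 12, 18 and 24, then every 9 weeks). Deaths were censored on the date of death.

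| q | Mean ratio of the two medians | Trials with identical medians |
|---|---|---|
| 3% | 1.046–1.053 | 78–84% |
| 10% | 1.125–1.145 | 43–54% |
| 20% | 1.256–1.310 | 9–18% |

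The time-to-progression median was never below the PFS median in the 9,000 trials. For scale, with a true median of 30 weeks the estimated PFS median had a 2.5–97.5 percentile range of 24–42 weeks.

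**6. Dependence on the censoring date.** Take a contrived set of 100 patients: 49 progress at week 12, 2 die at week 23 after a last assessment at week 6, and 49 progress at week 33.

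- PFS: S(12) = 0.51 and S(23) = 0.51 × 49/51 = 0.49, so the median is 23 weeks.
- Deaths censored at week 23: S stays at 0.51 until week 33, so the median is 33 weeks.
- Deaths censored at week 6: S(12) = 1 − 49/98 = 0.50, so the median is 12 weeks.

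The direction of the error is therefore fixed only once a censoring date is stated.

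**The case against.** The strongest reply is that the intent is clear from the rest of the protocol. Endpoint 3.3.1 requires patients to be alive, section 6.5.2 ends PFS follow-up at death, and the outcome is called progression-free survival. Nowhere does the plan say that deaths are censored; that is inferred from a missing phrase. This is right about intent. It does not repair the definition, because 3.3.1 is a proportion counted after the last dose and 6.5.2 is a rule for stopping follow-up. The analyst works from 13.1.

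The second reply is that the effect is small: a few percent at the anchor, identical medians in most simulated trials, and one descriptive secondary estimate in a trial of which section 13.2 says "we will not formally power for hypothesis testing". This stands and limits the weight of the point. Sampling error, however, has no fixed direction and shows in the confidence interval. The definitional shift, when deaths are censored on the date of death, goes one way and no interval reveals it.

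Third, the 3% does not estimate q. It omits deaths from other causes and does not say whether those patients had progressed, so it bounds q on neither side. This also stands: the omission is certain, its size is not.

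Fourth, the example in step 6 is fragile. It needs two patients who missed the week 12 and week 18 scans, and a curve exactly at 0.50. Under the midpoint convention its 12-week median becomes (12 + 33)/2 = 22.5 weeks, still just under 23. It shows only that the ordering is not guaranteed.

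**Conclusion.** The concern holds. As written, 13.1 gives a time-to-progression estimate under the name of PFS and does not deliver objective 2.2.1. It is most likely a drafting omission, and the definition is wrong as it stands, not merely short of detail.

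The likely effect is small: +3.1% to +4.5% on the median at the only anchor in the documents. That range assumes constant hazards, censoring on the date of death, and 70–100% of patients with an event. It would be larger if deaths without progression were more common, and the documents do not settle that. The primary endpoint, OS and the sample size are untouched. The missing censoring date and the wording of 3.3.1 are secondary; the missing death event is the substance of the point.

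**What to change.** In section 13.1, replace the PFS definition with wording such as:

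> PFS runs from the start of treatment to the first documented disease progression or death from any cause, whichever is earlier. Patients with neither event are censored at [a stated date, for example the last assessment showing no progression].

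Reword 3.3.1 so that it matches this definition and the median in 2.2.1. The sponsor should choose the censoring date, and how to treat progression reported by phone or record review, before the data are analysed.

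The cost is one phrase and one date in 13.1 and one line in 3.3.1. No new data collection is needed, since section 6.5.2 already provides: "All patients will be followed for OS status every 3 months, until death or off-study". Deaths after a patient goes off study may still be missed, as they would be for OS. The reported median PFS may come out slightly shorter.

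### Section 13.1 leaves death out of the PFS event, and its only named survival summary is a mean with no time limit although the objective is median PFS

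*Combined protocol and SAP*

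**What the plan says.** Section 13.1 (Secondary Analyses) defines the two survival times next to each other. OS runs to death from any cause or censoring. For PFS the text is: "PFS is calculated as the time between treatment start date until occurrence of disease progression or until censoring". Kaplan-Meier curves are planned for both. The next sentence gives the only numeric summary: "Proportional hazard modeling will be used to estimate mean survival time in both unadjusted and adjusted manners". It states no truncation time, and 13.1 mentions neither a median nor a confidence interval for PFS.

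Three other places bear on this:

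- Section 2.2.1, the objective: "Determine median PFS in the study population".
- Section 3.3.1, the endpoint: "Proportion of patients who are alive and have not had disease progression or relapse following last dose of study treatment".
- Section 6.5.2, on patients who stop treatment with stable disease or a response: they "remain in follow-up status for PFS by reported clinical status every 3 months until one of the following occurs: disease progression, relapse, or death".

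On stopping for toxicity, Section 2.2.3 reads "Determine the number of patients who discontinue treatment due to treatment-related AEs", and Section 3.3.3 repeats this as an endpoint. Section 13.1 adds times to toxicity, dose reduction and drug discontinuation as safety outcomes. These are to be shown as cumulative incidence curves, and no competing events are named.

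**The concern.** Section 13.1 is the text that an analyst will program. If PFS ends only at progression, a patient who dies without documented progression leaves the risk set as censored, as though still able to progress later. The curve then estimates something other than progression-free survival, and it always errs towards longer times. The trial is motivated by comparison with earlier results for the same combination (Section 1.3), so a PFS that excludes deaths would not be comparable with figures that include them.

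The mean raises a separate issue. A proportional-hazards model gives a mean only through a baseline survival curve integrated up to some time. Without a stated limit, that time is whatever follow-up exists at the data cut, or it depends on an unstated extrapolation. The quantity that the objective asks for, the median, is never named as the estimate to report.

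**Working it through.** **1. The plan's own figure.** The only precision figure in Section 13 is ±0.1 for the ORR at N = 100 and ORR 0.5. The Wald half-width is 1.96 × √(0.5 × 0.5 / 100) = 0.098. The Wilson interval at 50/100 is 0.404 to 0.596, half-width 0.096. The figure reproduces and is not in dispute. No precision is stated for PFS.

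**2. Is death a PFS event?**

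| Section | Death |
|---|---|
| 13.1, OS | event, any cause |
| 13.1, PFS | not named; only progression or censoring |
| 3.3.1 | patient must be alive to count |
| 6.5.2 | ends PFS follow-up, listed with progression and relapse |

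The 13.1 wording for PFS is the one that differs.

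**3. Size of the omission.** Inputs, all assumed: true median PFS 7 months (borrowed from the 7-month median treatment duration of the earlier trial in Section 9.2.11, so not a PFS figure); a fraction f of PFS events that are deaths without progression; Weibull shape k. The cumulative hazard of progression or death is ln2 × (t/7)^k. With deaths censored, only the share (1 − f) is left, so the curve reaches one half at 7 × (1/(1 − f))^(1/k).

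| f | k = 1 (constant hazard) |
|---|---|
| 5% | 7/0.95 = 7.4 months |
| 10% | 7/0.90 = 7.8 months |
| 20% | 7/0.80 = 8.8 months |

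Over f from 5% to 20%, the reading is 7.2 to 8.1 months at k = 1.5 and 7.6 to 10.2 months at k = 0.6.

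**4. The mean without a time limit.** With the median still fixed at 7 months, the unrestricted mean is 7 × Γ(1 + 1/k) / (ln2)^(1/k). This gives 19.4, 12.5, 10.1 and 8.1 months at k = 0.6, 0.8, 1 and 1.5. To see how far follow-up matters, 1,000 trials of 100 patients were simulated per setting. Accrual was uniform over 25 or 42 months, the ends of the range in Section 13.2 ("The total period of study recruitment is therefore anticipated to occur over a period of 25 to 42 months"). The data cut came 6 or 24 months after the last entry (assumed), and the Kaplan-Meier area was taken to the last observed time:

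| k | 25 / +6 | 25 / +24 | 42 / +6 | 42 / +24 |
|---|---|---|---|---|
| 0.6 | 11.7 | 14.2 | 14.0 | 15.7 |
| 0.8 | 10.5 | 11.7 | 11.6 | 12.1 |
| 1 | 9.5 | 10.0 | 9.9 | 10.1 |
| 1.5 | 8.0 | 8.1 | 8.1 | 8.1 |

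At k = 0.6 the data cut alone moves the mean by 14.2 − 11.7 = 2.5 months (25-month accrual) or 15.7 − 14.0 = 1.7 months (42-month accrual). At k = 1 the whole range is 10.1 − 9.5 = 0.6 months, and at k = 1.5 it is 0.1. The Kaplan-Meier median averaged 6.9 to 7.0 months in every setting. A mean restricted to 24 months is 10.4, 9.8, 9.2 and 8.0 months for the same shapes, whatever the data cut, provided that follow-up reaches 24 months.

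**5. Discontinuation for toxicity (clarification only).** Assume constant hazards, median time on treatment 7 months and 33% of stops due to toxicity. The 33% is the toxicity discontinuation rate in Section 1.3; using it as a share of stops is an assumption. At 12 months H = ln2 × 12/7 = 1.188. Cumulative incidence is 0.33 × (1 − e^(−1.188)) = 23%. If every other stop is censored, one minus Kaplan-Meier is 1 − e^(−0.33 × 1.188) = 32%.

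**The case against.** The strongest reply is that the PFS sentence is a drafting slip. The endpoint's name, Section 3.3.1 and Section 6.5.2 all point to death counting, and a sensible analyst would include it. That is probably what was meant. Section 3.3.1 is worded as a proportion after the last dose and Section 6.5.2 is a follow-up rule, so neither replaces the definition in 13.1. The conflict therefore stands and has to be settled in the text.

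On the mean, the reply is that Kaplan-Meier comes first in 13.1 and the median is read straight off that curve. This largely stands. A reader might infer that the plan cannot deliver the median; it can, but does not commit to reporting it with an interval. A reader might also infer that the mean is badly unstable. The widest spread in the table, 15.7 − 11.7 = 4.0 months, needs a long tail (k = 0.6) and changes accrual length and data cut together.

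On toxicity, a reader might infer that the discontinuation endpoint itself is biased. The documents do not support that. Section 3.3.3 asks for "Number of patients who discontinue treatment due to treatment-related AEs", and a count needs no censoring rule. The curves in 13.1 are additional, and cumulative incidence curves may already mean a competing-risk estimator.

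It is also tempting to say that progression is not captured as a reason for stopping, because the list in Section 6.4 omits it. Section 6.4 defers to a schema that is not in the available text, and Sections 3.1 and 9.1.4 both name progression, so that does not follow. Nor is a median OS owed: OS is not among the listed objectives or endpoints.

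**Conclusion.** The PFS definition in 13.1 is wrong as written and conflicts with Sections 3.3.1 and 6.5.2. Its effect is always to lengthen PFS: by 0.4 to 1.8 months on an assumed 7-month median at constant hazards, if 5% to 20% of PFS events are deaths without progression. The documents give neither the median nor that share, so the direction is certain and the size is illustrative.

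The mean without a time limit, set against an objective of median PFS, is a real but milder defect. Its dependence on follow-up is about 0.6 months or less at Weibull shape 1 or above, and material only with a long tail.

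The toxicity part is a request for clarification. The 32% against 23% applies only if a toxicity-specific curve is drawn with other stops censored, which the plan does not say.

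These are secondary and safety analyses in an estimation design. The primary ORR analysis, N = 100 and the ±0.1 margin are unaffected.

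**What to change.** In Section 13.1:

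1. Define PFS as the time from treatment start to progression or death from any cause, whichever comes first.
2. Name the Kaplan-Meier median PFS with its 95% CI as the estimate for objective 2.2.1.
3. If a mean is wanted, replace the proportional-hazards mean with a restricted mean to a pre-set time that follow-up will support (for example 24 months). Keep proportional-hazards models for covariate hazard ratios.
4. As clarification, report the 2.2.3/3.3.3 count as n/N with a CI. If a curve of time to discontinuation for toxicity is shown, use the Aalen-Johansen estimator, with death and stopping for other reasons, including progression, as competing events.

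The cost is a few sentences and slightly more analysis. Death already ends PFS follow-up (Section 6.5.2), and reasons for stopping are already recorded (Sections 6.4 and 6.5.2). There are two downsides. A restricted mean ignores time after its cut-off. The median will not be very precise at N = 100: a typical 95% CI is 5.1 to 9.1 months around 7 at shape 1.
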